#### ORTOPOD PILOT STUDY

#### **MARCH 1 2025**

**ORTOPOD PILOT STUDY** is a non-randomized, non-interventional clinical study that addresses the issue of perioperative neurocognitive disorder (deterioration of cognitive functions in the preoperative and perioperative period) and its impact on the occurrence of postoperative delirium.

Respondents meeting the entry criteria will undergo elective orthopaedic surgery (total hip arthroplasty) under general or regional anaesthesia. Preoperatively, they will be examined using the ALBA and POBAV tests, which serve for rapid and indicative assessment of cognitive functions. Furthermore, the functional capacity of patients will be assessed using the Clinical Frailty Scale, and depression will be evaluated using the Geriatric Depression Scale (questionnaire).

# After the procedure, during hospitalization in the ICU/PACU, screening for postoperative delirium will be conducted using the CAM-ICU tool.

The aim of the pilot study is to verify the methodology and obtain baseline data on the incidence of cognitive dysfunction, depression, and frailty preoperatively, as well as the incidence of postoperative delirium in this group of patients before submitting a grant to AZV ČR. The main research question will be whether preoperative cognitive decline (according to the ALBA and POBAV tests) is associated with the occurrence of postoperative delirium. The second research question will be what percentage of patients with preoperative cognitive deficit (according to the ALBA and POBAV tests) undergo elective total hip arthroplasty. Secondary outcomes will include whether there are differences in the ALBA and POBAV test results before and after surgery (cognitive decline after anesthesia and surgery), whether higher Clinical Frailty Scale scores are associated with the occurrence of postoperative delirium, and whether the results on the Geriatric Depression Scale change preoperatively and postoperatively.

Key words: postoperative delirium, screening, senior, risk factors, cognitive assessment, CAM-ICU, Amnesia Light and Brief Assessment (ALBA), POBAV

The study involves a homogeneous group of patients undergoing total hip arthroplasty under general or regional anesthesia. Patients meeting the study's entry criteria, who have signed informed consent to participate in the study, will be included.

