# **SECONDARY RESEARCH QUESTIONS:**

- Are higher values of the Clinical Frailty Scale before surgery (values 4, 5, or higher) associated with the worsening of cognitive functions?

- What is the percentage of patients with cognitive impairment according to the ALBA and POBAV tests before knee and hip arthroplasty surgery in hospitals?
- Are the results different in the ALBA and POBAV tests in the period before and after the surgery?
- Are higher values on the Clinical Frailty Scale before surgery (values 4, 5, or higher) associated with a deterioration in cognitive functions?

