#### DATA COLLECTION TOOLS AND PROCEDURES

#### **Preoperatively:**

- Cognitive test ALBA and POBAV
- Clinical Frailty Scale

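### The before/after outcomes for ALBA/POBAV and for the Geriatric Depression Scale have no postoperative measurement listed or timed in the data collection section

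*Protocol*

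**What the plan says.** The paragraph on the aim of the pilot names three secondary outcomes. Two of them compare the same patient before and after surgery:

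- for cognition, "whether there are differences in the ALBA and POBAV test results before and after surgery (cognitive decline after anesthesia and surgery";
- for depression, "whether the results on the Geriatric Depression Scale change preoperatively and postoperatively".

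The third relates the Clinical Frailty Scale to delirium. The Secondary research questions repeat the cognitive comparison ("Are the results different in the ALBA and POBAV tests in the period before and after the surgery") and ask twice about frailty and cognition, once as "associated with the worsening of cognitive functions" and once as "associated with a deterioration in cognitive functions".

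The GDS is clearly meant to be given before surgery. The opening description of the preoperative examination says that "depression will be evaluated using the Geriatric Depression Scale (questionnaire", and the aim is to "obtain baseline data on the incidence of cognitive dysfunction, depression, and frailty preoperatively".

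The section Data collection tools and procedures says what is collected and when. Under Preoperatively it has "Cognitive test ALBA and POBAV" and the Clinical Frailty Scale. Under Postoperatively it has CAM-ICU and nothing else. The lists for ICU, for PACU and for patients who develop delirium then give times for screening.

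**The concern.** A before/after outcome needs the same instrument twice, and the second time must be defined. Here the outcomes are stated, but the section that tells staff what to do and when gives no second administration. Which instruments patients receive, and at what time, belongs in the protocol. An analysis plan can define how change is analysed, but it cannot supply a test that was not given.

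Two things are at stake. If staff work from the data collection section alone, the postoperative ALBA, POBAV and GDS are not done and neither change can be estimated. If staff infer from the outcomes that a repeat is wanted, each site must choose the time. A test a few hours after anaesthesia can reflect residual drug effect or delirium, while a later one is closer to the decline after anaesthesia and surgery that the outcome names. Mixing such times gives a change score with no single meaning. The purpose of this pilot is to verify the methodology before a grant application, so a gap in the assessment schedule bears directly on that purpose.

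**Working it through.** The protocol gives no figure to reproduce on this point. The check sets each question against the data collection section.

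**Step 1. Questions and what they need.** The aim paragraph, the Main research question and the Secondary research questions together pose six distinct questions. This count treats the hip-only and the knee-and-hip wordings of the prevalence question as one, and the duplicated frailty–cognition question as one.

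| Question | Postoperative instrument needed | Listed? |
|---|---|---|
| Preoperative ALBA/POBAV and delirium (main) | CAM-ICU | yes |
| Prevalence of preoperative deficit | none | not applicable |
| Frailty and delirium | CAM-ICU | yes |
| ALBA/POBAV before and after | ALBA, POBAV | no |
| GDS before and after | GDS | no |
| Frailty and worsening cognition | ALBA, POBAV, if worsening means before-to-after change | no |

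Result: 3 unaffected + 2 affected + 1 affected under one reading = 6. Within the aim paragraph's own list, 2 of 3 secondary outcomes are affected.

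**Step 2. Measurements listed in the data collection section.**

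- ALBA/POBAV change: preoperative yes, postoperative no, so 1 of 2.
- GDS change: preoperative no, postoperative no, so 0 of 2. The preoperative one is intended elsewhere in the protocol, so that half is a list omission.
- Postoperative instruments needed across the questions: CAM-ICU, ALBA, POBAV and GDS. Listed: CAM-ICU, so 1 of 4.
- Stated times for a postoperative ALBA, POBAV or GDS anywhere in the protocol: 0.

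**Step 3. Could the word screening cover these tests?** The protocol ties postoperative screening to delirium and CAM-ICU, first in the sentence that introduces the postoperative phase and again in the Postoperatively list. The delirium list uses the word in the same sense. Nothing extends it to ALBA, POBAV or GDS.

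**Step 4. If it did, would the time be fixed?** No. The screening times are 4 hours after general anaesthesia, day 1, day 2 and, in the ICU, discharge. The exit screening is day 2 in the PACU list but discharge from the unit in the ICU list. Attaching the tests to it would give the two groups different times.

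**The case against.** The strongest reply is that the data collection section is silent and forbids nothing. It also omits the preoperative GDS, which the protocol plainly intends, so it is an incomplete list, and an incomplete list is weak evidence that a missing test will not be done. The outcomes themselves commit the study to a repeat, and sites may well carry one out.

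This stands in part. A reader might infer that the schedule rules out postoperative testing, or that both outcomes are certain to be lost. The document supports neither inference. Loss is one of two possible consequences and uncontrolled timing is the other. The reply does not remove the defect, because a site that infers the repeat still finds no time for it.

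A reader might also infer that the exclusion for drug effect at cognitive testing would invalidate a postoperative test. That item is an eligibility criterion that begins with premedication, and the protocol nowhere applies it to follow-up. Residual drug effect is a reason to fix the time, but that criterion does not create the problem.

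Finally, the different exit screenings govern CAM-ICU. They matter here only because they cannot serve as a ready-made common time for the other tests.

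**Conclusion.** The point holds as a promise that is neither listed nor timed. Two of the three secondary outcomes in the aim paragraph, and the matching secondary research question, lack a scheduled second measurement. The frailty–cognition question is affected only if worsening or deterioration means change from before to after surgery, which the protocol does not say. The missing preoperative GDS is a smaller omission in the list.

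A reader might extend this to the study's main result, but the documents do not support that. The main question needs preoperative ALBA/POBAV and postoperative CAM-ICU, and both are listed. The prevalence question and the frailty–delirium outcome are likewise unaffected.

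The conclusion rests on reading screening as CAM-ICU screening, which is how the protocol uses the word. The bias from mixed timing cannot be sized, because the protocol gives no score distributions, delirium rates or lengths of stay. The point should be fixed before enrolment, or as early as possible if enrolment has begun, since a postoperative test that is not given at its time cannot be recovered.

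**What to change.** Reconcile the outcomes with the data collection section in one of two ways.

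1. **If the repeat is intended:** add ALBA, POBAV and GDS to the Postoperatively list at one fixed time point with a stated window. Make it the same for ICU and PACU patients, and do not define it by the exit screening. Say that the test is due at that time even if the patient has already left the unit.
2. **If it is not intended:** delete the two change outcomes from the aim paragraph and the ALBA/POBAV before/after question from the Secondary research questions.

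In either case, add the GDS to the Preoperatively list so that it agrees with the opening description, and state whether worsening in the frailty question means change from before to after surgery.

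The second option costs wording only. The first adds one short bedside repeat of tests that the protocol already promises, possibly on the ward for patients who have left the ICU or PACU. The protocol gives no staffing or length-of-stay figures, so that effort cannot be quantified.

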## **Postoperatively**

• CAM-ICU (screening at least once a day) during hospitalization in the ICU

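### The uncontrolled before/after change in ALBA and POBAV is labelled as cognitive decline, although true change cannot be separated from a retest effect and no postoperative test session is scheduled

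*Protocol*

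**What the plan says.** The aim of the pilot study, in the Protocol's introductory text, lists among the secondary outcomes "differences in the ALBA and POBAV test results before and after surgery (cognitive decline after anesthesia and surgery"). The list of secondary research questions puts the same comparison neutrally: "Are the results different in the ALBA and POBAV tests in the period before and after the surgery".

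On design, the introductory text states: "The study involves a homogeneous group of patients undergoing total hip arthroplasty under general or regional anesthesia". The entry criteria likewise admit only operated patients, and no unoperated or other comparison group appears anywhere.

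On the instruments, the opening section speaks of the "ALBA and POBAV tests, which serve for rapid and indicative assessment of cognitive functions". The key words expand ALBA as Amnesia Light and Brief Assessment.

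On timing, the section on data collection tools lists "Cognitive test ALBA and POBAV" under Preoperatively, with no version. Under Postoperatively the only entry is "CAM-ICU (screening at least once a day) during hospitalization in the ICU". The ICU and PACU schedules that follow (day 0, day 1, day 2, exit) are for screening and are not said to include ALBA or POBAV.

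**The concern.** When one group is tested twice with the same named instruments, the second score can differ from the first because the patient's state has changed or because the patient has met the test before. For a test that is by its name an assessment of amnesia, prior exposure plausibly helps. That gain runs in the opposite direction to the decline the protocol is looking for.

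The consequences differ by result:

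- **No change or improvement.** It could mean no decline, or a decline offset by a practice gain. It cannot be interpreted.
- **A fall.** It would suggest decline, and would understate it if there were a practice gain. Without a comparator it could not be put down to anaesthesia and surgery rather than to anything else that differed between the sittings.

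A second outcome may be touched. The secondary research questions ask whether higher Clinical Frailty Scale values go with worsening of cognitive function. If that is answered with this change score, and practice gain differs by frailty, the comparison is distorted as well.

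The pilot is meant to verify the methodology before a grant application, so a weakness here would carry into the larger study.

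**Working it through.** The protocol states no sample size, effect size, SD or test-retest figure for these tests, so there is no figure of its own to reproduce. The check sets out what the design can identify and then illustrates size on assumed values.

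**1. What is identified.** Let D be the true mean decline and P the mean practice gain, both in SDs of the change score. In one group without a comparator:

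observed mean decline = D − P

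There is one equation and two unknowns. The documents supply no second source (control group, alternate form, retest norm) to separate them. This holds at any retest interval; the interval affects only how large P is likely to be.

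**2. Size of masking, on assumed values.** If D = 0.3, a gain of 0.2 leaves 0.3 − 0.2 = 0.1, and a gain of 0.3 leaves 0.3 − 0.3 = 0.

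**3. Chance of a significant decline, on assumed values.** For a paired z-test at two-sided 5%:

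Pr(significant decline) = Φ((D − P)·√n − 1.96)

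Worked case, n = 50, D = 0.5, P = 0.2: 0.3 × 7.071 − 1.96 = 0.161, and Φ(0.161) = 56%.

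| Practice gain P (SD) | n = 50, D = 0.5 | n = 50, D = 0.3 | n = 100, D = 0.3 |
|---|---|---|---|
| 0 | 94% | 56% | 85% |
| 0.1 | 81% | 29% | 52% |
| 0.2 | 56% | 10.5% | 17% |
| 0.3 | 29% | 2.5% | 2.5% |
| 0.5 | 2.5% | below 0.1% | below 0.1% |

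In the last column, a gain of 0.5 SD gives a 52% chance of a significant apparent improvement despite a true decline of 0.3 SD.

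**4. Frailty comparison, on assumed values.** Suppose frail and non-frail patients both truly decline by 0.3 SD, and the gain is 0 in frail and 0.3 SD in non-frail patients. The observed declines are 0.3 − 0 = 0.3 and 0.3 − 0.3 = 0, a spurious difference of 0.3 SD. This simply returns the assumed gap in gains. It shows the direction of the distortion and is not evidence that the gap exists.

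**5. Timing.** The outcome needs a postoperative ALBA and POBAV. The data collection sections provide one preoperative entry for the tests and no postoperative one, so neither the interval nor the form used at the second sitting can be read from the protocol.

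**The case against.** The case on the other side has real weight.

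- **A short interval is not stated.** A reader might infer that the two sittings fall within days, in one admission. The days given belong to the postoperative screening schedules, and no ALBA or POBAV session is attached to them.
- **Reuse of identical items is not stated.** A reader might infer that patients see the same items twice. The protocol is silent on versions, and a test manual or working procedure might settle it. Carry-over is plausible here, not shown.
- **POBAV is not described as a memory test.** Only ALBA's name supports that reading; both tests are otherwise described only as rapid cognitive assessments.
- **The outcome is not worthless.** It is tempting to say that the difference can never be read as decline. That goes too far: a practice gain works against a fall, so an observed fall would still suggest decline.
- **Regression to the mean does not bias the whole-group change.** Patients are not selected on baseline ALBA or POBAV score. It would matter only for subgroups defined by a low first score, and no such comparison of change is listed.
- **The label may be purely temporal.** The word used is after, not because of, and the secondary research question is neutral. Even so, the parenthesis equates a difference in score with decline.
- **The sizes are assumed.** With a gain of 0 to 0.1 SD the masking is smaller, although in the table 0.1 SD still takes 85% to 52% in one case.
- **This is one secondary outcome of a pilot.** The main question and the percentage with preoperative impairment use only the preoperative tests.

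What stands is the single operated group, the lack of any stated comparator, alternate form or retest reference, and the unscheduled second test. A later analysis plan cannot repair these without outside retest data, because form and timing are fixed when the data are collected.

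**Conclusion.** The point holds in a limited form. The protocol labels an uncontrolled before/after difference as cognitive decline while fixing neither when the second test is done nor which form is used, and it gives no reference for retest effects. No change or improvement would be uninterpretable. A fall would suggest decline, without attribution to anaesthesia and surgery.

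The size cannot be derived from the protocol. On the assumed values, a gain of 0.2 to 0.3 SD reduces a 94% chance of detecting a 0.5 SD decline in 50 patients to between 56% and 29%; a gain near zero would do little. Any effect on the frailty question is conditional on that question using the change score and on practice gain differing by frailty. This is a cheap improvement to a secondary outcome, worth making before the methodology is carried into the grant application.

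**What to change.** 1. Add a postoperative ALBA and POBAV session to the data collection section, with its time fixed.
2. Where equivalent alternate forms of a test exist, use a different form at each sitting, alternate the order across patients, and record the version.
3. Where they do not exist, describe the outcome in the aim as uncontrolled net change including retest effect, remove the parenthetical label, and state that absence of decline is inconclusive.

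Alternate forms reduce memory for items but not familiarity with the task, and they do not supply a comparator. Even with them, the report should not attribute change to anaesthesia and surgery.

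The cost is a second set of test sheets and one recorded field. If the forms differ somewhat in difficulty, alternating the order balances this on average, at the price of slightly more variance. The wording change is free.

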# MAIN RESEARCH QUESTION

- The main research question of the ORTOPOD PILOT STUDY is whether preoperative cognitive decline, as assessed by the ALBA and POBAV tests, is associated with the occurrence of postoperative delirium in the Czech Republic?

# **SECONDARY RESEARCH QUESTIONS:**

- Are higher values of the Clinical Frailty Scale before surgery (values 4, 5, or higher) associated with the worsening of cognitive functions?

- What is the percentage of patients with cognitive impairment according to the ALBA and POBAV tests before knee and hip arthroplasty surgery in hospitals?
- Are the results different in the ALBA and POBAV tests in the period before and after the surgery?
- Are higher values on the Clinical Frailty Scale before surgery (values 4, 5, or higher) associated with a deterioration in cognitive functions?

#### DATA COLLECTION TOOLS AND PROCEDURES

#### **Preoperatively:**

- Cognitive test ALBA and POBAV
- Clinical Frailty Scale

## **Postoperatively**

• CAM-ICU (screening at least once a day) during hospitalization in the ICU

## **ICU Hospitalization:**

• 0th postoperative day (4 hours after general anesthesia), 1st postoperative day, 2nd postoperative day, screening during ICU hospitalization, final screening upon discharge from ICU = exit screening

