## **PACU Hospitalization:**

• 0th postoperative day (4 hours after general anesthesia), 1st postoperative day, 2nd postoperative day = exit screening

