## **ENTRY CRITERIA:**

- Age over 65 years (inclusive)
- Type of procedure: elective total hip arthroplasty under general or regional anesthesia
- ASA classification I-III
- Absence of sensory impairment (blindness, deafness, deaf-muteness)
- Postoperative hospitalization in the intensive care unit, post-anesthesia care unit (PACU)

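### Delirium is screened to ICU discharge in one unit but only to postoperative day 2 in the other, so the main outcome has no common observation window

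*Protocol*

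**What the plan says.** The Protocol sets the screening schedule by unit.

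- **ICU Hospitalization:** screens on days 0, 1 and 2, then "screening during ICU hospitalization, final screening upon discharge from ICU = exit screening". No maximum day is given.
- **PACU Hospitalization:** the same day 0 screen, then "1st postoperative day, 2nd postoperative day = exit screening". Screening ends there.
- **Postoperatively:** "CAM-ICU (screening at least once a day) during hospitalization in the ICU".
- **The section headed by the sentence on screening after the procedure:** "during hospitalization in the ICU/PACU, screening for postoperative delirium will be conducted using the CAM-ICU tool", which ties screening to the unit stay.
- **Entry Criteria:** patients from the ICU and from the PACU are both eligible and form one population.

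The outcome itself carries no window. The Main Research Question asks whether preoperative cognitive decline "is associated with the occurrence of postoperative delirium in the Czech Republic". The aims call for baseline data on cognition, depression and frailty, "as well as the incidence of postoperative delirium in this group of patients before submitting a grant to AZV ČR".

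**The concern.** Up to day 2 the two schedules list the same screens. After day 2 an ICU patient who is still free of delirium can go on to be counted, while a PACU patient cannot. Before day 2 the windows may differ too, in either unit, because screening is tied to the stay and nothing says whether the day 1 and day 2 screens are done once a patient has left.

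Two results are exposed:

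- **The main association.** The study is non-randomized, so the design does not balance unit or length of stay between impaired and unimpaired patients. If either is related to cognition or frailty, window length alone can create an association or hide one.
- **The incidence.** If any ICU patient stays past day 2, the pooled figure averages over windows of different length, whatever the link with cognition. It then refers to no defined period, which makes it a poor planning figure for the grant application.

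**Working it through.** The protocol states no delirium rate, length of stay, ICU share or sample size, so there is no figure of its own to reproduce. The unequal windows follow from the text; the size below rests on assumptions.

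**Assumed inputs.** The daily probability of a first positive screen is the same in both units and for impaired and unimpaired patients, so there is no true effect.
- Falling risk, days 0 to 4: 4%, 5%, 3%, 1.5%, 1%.
- Constant risk: 5% per day (2% and 10% as sensitivity values).

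**Step 1. Cumulative detection = 1 − ∏(1 − daily risk)**

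| Window | Falling | Constant 5% |
|---|---|---|
| Days 0-1 | 1 − 0.96×0.95 = 0.0880 | 1 − 0.95² = 0.0975 |
| Days 0-2 | 1 − 0.96×0.95×0.97 = 0.1154 | 1 − 0.95³ = 0.1426 |
| Days 0-4 | 1 − 0.96×0.95×0.97×0.985×0.99 = 0.1373 | 1 − 0.95⁵ = 0.2262 |

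**Step 2. Longer ICU window more common in impaired patients.** Group risk = p × (days 0-4) + (1 − p) × (days 0-2), where p is the share with the longer window.

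- p = 40% impaired, 10% unimpaired, falling: 0.4×0.1373 + 0.6×0.1154 = 0.1242 against 0.1×0.1373 + 0.9×0.1154 = 0.1176. OR = (0.1242/0.8758)/(0.1176/0.8824) = 1.06.
- Same split, constant 5%: 0.1761 against 0.1510, OR 1.20. At 2% and 10% per day the OR is 1.19 and 1.22.
- p = 70% against 10%: falling 0.1307 against 0.1176, OR 1.13; constant 5%, OR 1.42; constant 10%, 0.3680 against 0.2849, OR 1.46.
- Equal p in both groups: OR 1.00.

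**Step 3. Reversed direction.** Suppose screening stops at unit exit, and 40% of impaired against 10% of unimpaired patients leave before the day 2 screen.

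- Falling: 0.4×0.0880 + 0.6×0.1154 = 0.1044 against 0.1126, OR 0.92.
- Constant 5%: 0.1246 against 0.1381, OR 0.89.

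**Step 4. Pooled incidence** when 0%, 25% or 50% of all patients have the longer window:

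- Falling: 11.5%, 12.1%, 12.6%.
- Constant 5%: 14.3%, 16.4%, 18.4%.

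**Step 5. Delirium lost from a day 0-2 outcome,** as a share of five-day detections in long-stay ICU patients:

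- Falling: (0.1373 − 0.1154)/0.1373 = 16%.
- Constant 5%: (0.2262 − 0.1426)/0.2262 = 37%.

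**Second set of assumptions.** Daily risk is flat 3%, flat 5%, or declining (8, 5, 4, 3, 2, 1, 1, 1%). ICU shares are 60% against 30%, or 80% against 20%. ICU screening ends on day 3, 5 or 7, and there is again no true effect. The risk ratio from window length alone is 1.05-1.18, 1.08-1.46 and 1.11-1.68 respectively. A fully observed day 0-2 window gives 1.00 throughout.

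**The case against.** The strongest reply is that the outcome rule belongs in the SAP, which is not shown. Days 0, 1 and 2 are planned for both units, later ICU screens are extra data, and nothing says that all screens will be pooled regardless of day. In part this stands: an SAP could cut the outcome off at day 2. It could not recover day 1 or day 2 screens that were never done because the patient had left the unit, and that rule sits in the protocol's schedule.

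A second reply is that the bias is conditional and may be small. This is true. It needs a link between cognition and unit or stay, which the protocol does not report, and the milder case gives an OR of only 1.06. An OR of 1.46 needs both the 70% against 10% split and a constant 10% daily risk. A pilot will also be imprecise. Assuming 50 patients per group and 12% delirium in each (6 events, 44 non-events), the standard error of the log OR is √(2/6 + 2/44) = 0.615, and the 95% interval around 1.00 is about 0.30 to 3.3. That limits how far the bias could change this study's conclusion on the association. It does not give the incidence a defined period.

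Third, a day 0-2 outcome gives up later episodes, and screening patients after they leave the unit is fieldwork as well as wording. Both points stand and are counted as costs. So does the point that at-least-daily ICU screening leaves intensity variable within days 0-2.

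**Conclusion.** The concern holds, and the schedule should be corrected. The text sets an open-ended window for ICU patients and a closed one for PACU patients, pools them, and gives the outcome no period of its own.

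The effect on the main association is unknown in size and direction. Under the assumptions above, unequal windows alone give odds ratios from 1.06 to 1.46 when impaired patients are observed longer, 0.89 to 0.92 when they lose the day 2 screen more often, and 1.00 when unit and stay are unrelated to cognition. With half the patients on the longer window, pooled incidence rises from 11.5% to 12.6% (falling risk) or from 14.3% to 18.4% (constant 5%). The unequal windows are certain from the text; confidence that they matter materially is medium, because every rate, share and stay used here is assumed.

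**What to change.** 1. Define the main delirium outcome as at least one positive CAM-ICU from day 0 to the end of postoperative day 2, for every patient and in either unit. Use the same window for the incidence.
2. Keep the later ICU screens and report them separately as descriptive data.
3. Reconcile the ICU, PACU and Postoperatively sections with the opening description, so that it is clear whether the day 1 and day 2 screens are done for patients who leave the ICU or PACU before day 2. The common window equalises observation only if those screens are done or their absence is handled.
4. Report the number of completed screens per patient by cognitive status, which would also show differences in screening intensity within days 0-2.

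**Cost.** One outcome definition and one clarifying sentence in the schedule; the day 0-2 screens are already listed for both units. If screening is to continue after early unit exit, there is staff time outside the ICU and PACU as well. Delirium first detected after day 2 moves to a secondary description: under the assumed risks, 16% to 37% of the five-day detections in long-stay ICU patients.
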